7.2.7 Serious Adverse Events

The Investigator is required to determine if each AE is a Serious Adverse Event (SAE). An SAE is any AE occurring after randomization and through Day 28 and results in any of the following outcomes:

- Death, or
- Is life-threatening, or
- Prolongation of existing hospitalization, or
- Results in a persistent or significant incapacity or substantial disruption of the ability to conduct normal life functions, or
- Is a congenital anomaly/birth defect.

Important medical events that may not result in death, be life threatening, or require hospitalization may be considered SAEs when, based upon appropriate medical judgment, they may jeopardize the patient and may require medical or surgical intervention to prevent one of the outcomes listed in this definition.

In the event of death, the cause of death should be recorded as the SAE (death is an outcome, not the AE itself).

Any planned procedures that require admission to hospital as well as any planned elective procedures (e.g., angioplasty) are not considered SAEs (unless the underlying condition has worsened or the procedure results in a worsening of the patient's condition). In addition, pregnancy that occurs during the course of the study or absence of a treatment effect will also not be considered to be an SAE and will be collected on a separate CRF.

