6.2 Secondary Endpoints

- 1. Improvement in oxygenation defined as any one of the following:
 - Stabilization of PaO2/FIO2 >250
 - Improvement in FIO2 by 50% or improvements ≥15% in S/F, P/F ratio from baseline at 12 hours, Day 5 and Day 10 (or end of treatment)
- 2. Improved clinical outcomes defined as one of more of the following:
 - Time to extubation following the site's extubation protocol

- Free from re-intubation
- Reduction in ICU days
- Reduction in the number of re-admissions to the ICU due to COVID-19 within 28 days
- Reduction in total hospital days
- Mortality [28 days] defined as Cardiopulmonary mortality from all causes

3. Safety and tolerability

 Monitoring of adverse events (AEs), serious adverse events (SAEs), chest CT or Chest X-rays, vital signs, ventilatory/oxygenation parameters, and laboratory tests.

6.3 Exploratory endpoints will include (where available as part of standard of care):

- Change in LDH
- Change in fibrinogen
- Change in WBC count including lymphocytes and neutrophil subsets
- Change in triglycerides
- Change in ferritin
- Change in CRP / ESR
- Change in IL-6
- Change in D-Dimer

Changes in these parameters will be assessed for each patient from baseline to end of study as well as changes between the active and control groups.

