7.2.8 Reporting for SAEs (24 Hours)

Regardless of causality, an SAE must be followed clinically until resolution or stabilization.

All SAEs after randomization and through Day 28 of the study must be reported to the Sponsor or the Sponsor's representative within 24 hours of the investigational site's knowledge of the occurrence. The investigational site will email a Serious Adverse Event Report (SAER) to the Sponsor and the Medical Monitor. Investigational sites will be provided with SAER forms. The Medical Monitor will work closely with the Sponsor to properly assess and report the SAE.

The SAE information emailed to the Sponsor or the Sponsor's representative will include the following (as available):

- Patient Number, Investigator name, and Site Number
- SAE information: event term, onset date, severity, and causal relationship
- Basic demographic information (e.g., age, gender, weight)
- The outcomes attributable to the event (death, a life-threatening adverse drug experience, inpatient hospitalization or prolongation of existing hospitalization, a persistent or significant disability/incapacity, other important medical event[s])
- A summary of relevant test results, pertinent laboratory data, and any other relevant medical history
- The first and last dates of study drug administration.
- A statement whether study medication was discontinued or study medication administration schedule modified
- A statement whether event recurred after reintroduction of study medication if administration had been discontinued or withheld
- Supplemental anonymized information may include the following hospital records: laboratory results, radiology reports, progress notes, admission and emergency room notes, holding/observation notes, discharge summaries, autopsy reports, and death certificates

Supplemental information may be transmitted using a follow-up report and should not delay the initial report.

For regulatory purposes, initial reports of SAEs should be transmitted within the prescribed time frame as long as the following minimum information is available: patient number, suspect study medication, reporting source, and an event or outcome that can be identified as being both serious and unexpected for which the Investigator can make a relationship assessment.

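### Section 7.2.7 counts prolonged but not new hospitalization as serious, which contradicts Section 7.2.8 and other sentences in 7.2.7

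*Combined protocol and SAP*

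**What the plan says.** The references are to the last of the protocol versions in the combined document, the current one. Section 7.2.7 opens with "An SAE is any AE occurring after randomization and through Day 28 and results in any of the following outcomes" and gives five: death, threat to life, prolonged hospital stay, lasting or significant incapacity, and congenital anomaly. The hospital bullet reads "Prolongation of existing hospitalization, or".

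Two further sentences of 7.2.7 bear on the point. The important-medical-event sentence begins "Important medical events that may not result in death, be life threatening, or require hospitalization may be considered SAEs when", and it applies where the event may jeopardize the patient and "may require medical or surgical intervention to prevent one of the outcomes listed in this definition". A later paragraph exempts planned procedures that involve a hospital admission from being SAEs.

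Section 7.2.8 sets a 24-hour reporting duty for SAEs from randomization to Day 28. The items to be sent to the sponsor include: "The outcomes attributable to the event (death, a life-threatening adverse drug experience, inpatient hospitalization or prolongation of existing hospitalization, a persistent or significant disability/incapacity".

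**The concern.** The definition and the report content disagree on whether a new inpatient admission is a serious outcome. The definition governs. Section 7.2.8 says what to send once an event is already classed as an SAE, so its longer list does not make an event serious.

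The event at issue is an unplanned readmission after discharge and before Day 28 that is not fatal, life-threatening or incapacitating. Under 7.2.7 the admission itself does not make the event serious. Whether the sponsor hears of it within 24 hours, and whether it enters the SAE summary under Section 10.8, is left to the judgment of the person classifying it. The study stopping rule in Section 4.4.1 is no substitute, because it counts patients removed under criteria that apply during study drug administration. For events after discharge, SAE reporting is the main expedited route to the sponsor.

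**Working it through.** There is no planned figure to reproduce. The check is a comparison of text, followed by simple arithmetic on scale.

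**1. The two lists side by side**

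| Outcome | 7.2.7, definition | 7.2.8, report content |
|---|---|---|
| Death | yes | yes |
| Life-threatening | yes | yes |
| Prolonged existing stay | yes | yes |
| New inpatient hospitalization | **no** | **yes** |
| Lasting or significant incapacity | yes | yes |
| Congenital anomaly | yes | no |
| Other important medical event | separate sentence, discretionary | yes |

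The point rests on the fourth row. No other section of the current version adds new hospitalization to the definition. The same five-item list stands in the three superseded versions in the combined document, so the gap is not an accident of text extraction.

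**2. What the rest of 7.2.7 presupposes**

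- The important-medical-event sentence sets its events apart from those that do meet a criterion, and names needing hospitalization as one such criterion. The list has no such item.
- An exemption for planned admissions has a purpose only if unplanned ones would otherwise count.

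**3. Whether the case can arise**

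- Every patient is ventilated in hospital at entry, so an event before discharge can prolong the stay but cannot cause a new one.
- Treatment lasts at most 10 days and SAE reporting runs to Day 28, which leaves 28 − 10 = 18 days or more after treatment.
- Section 2.2.5 names earlier discharge as a possible benefit, and Section 6.2 includes fewer total hospital days among the secondary outcomes. Section 7.2.8 lists discharge summaries and emergency room notes among the supporting records.
- An admission after discharge starts a new hospitalization and does not prolong the earlier one.

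**4. Whether the fallback closes the gap**

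The important-medical-event route is permissive, since such events may be considered SAEs. It is also tied to preventing an outcome on the list. It can catch a readmission where the event threatened death or another listed outcome. It cannot catch one on the ground of admission, because admission is not listed.

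**5. Scale**

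- Section 3.3 plans 10 patients per arm. One patient with no other SAE who moves from AE to SAE changes that arm's SAE incidence by 1/10 = 10 percentage points.
- As a rough ceiling on who could be exposed, apply the mortality of 22% to 62% that Section 2.1 reports for critically ill patients to about 20 patients. This is an assumption, because that section gives no time horizon. Survivors would number 20 × (1 − 0.62) = 7.6 to 20 × (1 − 0.22) = 15.6, roughly 8 to 16. Only some would be discharged by Day 28, fewer would be readmitted, and fewer still would meet no other criterion.
- The documents give no discharge or readmission rates, so no expected count can be calculated.

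**The case against.** The strongest reply is that this is a drafting slip. Patients are inpatients at entry, which probably explains the bullet, and the surrounding sentences show that unplanned admission was meant to count, so a sensible investigator would report it. That is a fair reading of intent. It does not settle the matter, because the operative list omits the item and the only other route is discretionary.

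Three further replies stand in part:

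- **The event is not lost.** Section 7.2.1 has all AEs recorded from first dose to Day 28, and Section 9.1.3 assesses AEs and SAEs at Day 28. What is at risk is the seriousness label and the expedited report.
- **Late reporting has another cause.** The 24-hour clock starts when the site learns of the event, and the schedule has no visit between Day 10 and Day 28. A corrected definition does not change that.
- **The SAE report form is not in the documents.** It may already list hospitalization, but a form does not amend the definition.

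A reader might also take the secondary outcome "Reduction in the number of re-admissions to the ICU due to COVID-19 within 28 days" as proof that the protocol foresees discharge and return. It is not proof, because a patient can go back to the ICU from a ward within one hospital stay, where the prolongation bullet may apply. The sections cited in step 3 of the working are the better support.

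**Conclusion.** The point holds as an internal inconsistency that is wrong as written. Section 7.2.7 omits new inpatient hospitalization, in conflict with 7.2.8 and with two of its own sentences. The consequence is limited to unplanned readmissions after discharge and by Day 28 that meet no other seriousness criterion. These are recorded as AEs, but their 24-hour report and SAE count depend on discretion. The number affected is unknown and probably small. No sample size, power or alpha figure is touched.

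Three stronger readings go beyond the documents:

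- A reader might infer that readmissions can never be SAEs. Fatal, life-threatening or incapacitating ones are, and others may be classed as important medical events.
- A reader might infer that the under-count falls on the arm that does better, because its patients spend longer out of hospital. Those patients may also be less likely to return. The direction is unknown, and the documents have no data on it.
- A reader might measure the gap by the share of the 28 days spent after discharge. That needs an assumed discharge day, and it measures time, not missed SAEs.

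**What to change.** In Section 7.2.7, change the hospital bullet so that an event is serious if it requires "inpatient hospitalization or prolongation of existing hospitalization". This uses the phrase already in 7.2.8. Keep the exemption for planned admissions, and check that the SAE report form and its instructions use the same list.

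The same edit should make clear how the sentence in 7.2.7 that excludes lack of treatment effect applies to a readmission for worsening COVID-19. Otherwise such an event could still be argued out of the SAE count.

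The cost is one bullet, one clarification and possibly a few more SAE reports. No endpoint, analysis or sample size changes. The fix does not remedy the absence of scheduled contact between Day 10 and Day 28, so a readmission may still come to the site's notice late.

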7.2.8 Reporting for SAEs (24 Hours)

Regardless of causality, an SAE must be followed clinically until resolution or stabilization.

All SAEs after randomization and through Day 28 of the study must be reported to the Sponsor or the Sponsor's representative within 24 hours of the investigational site's knowledge of the occurrence. The investigational site will email a Serious Adverse Event Report (SAER) to the Sponsor and the Medical Monitor. Investigational sites will be provided with SAER forms. The Medical Monitor will work closely with the Sponsor to properly assess and report the SAE.

The SAE information emailed to the Sponsor or the Sponsor's representative will include the following (as available):

- Patient Number, Investigator name, and Site Number
- SAE information: event term, onset date, severity, and causal relationship
- Basic demographic information (e.g., age, gender, weight)
- The outcomes attributable to the event (death, a life-threatening adverse drug experience, inpatient hospitalization or prolongation of existing hospitalization, a persistent or significant disability/incapacity, other important medical event[s])
- A summary of relevant test results, pertinent laboratory data, and any other relevant medical history
- The first and last dates of study drug administration.
- A statement whether study medication was discontinued or study medication administration schedule modified
- A statement whether event recurred after reintroduction of study medication if administration had been discontinued or withheld
- Supplemental anonymized information may include the following hospital records: laboratory results, radiology reports, progress notes, admission and emergency room notes, holding/observation notes, discharge summaries, autopsy reports, and death certificates

Supplemental information may be transmitted using a follow-up report and should not delay the initial report.

For regulatory purposes, initial reports of SAEs should be transmitted within the prescribed time frame as long as the following minimum information is available: patient number, suspect study medication, reporting source, and an event or outcome that can be identified as being both serious and unexpected for which the Investigator can make a relationship assessment.

7.3 Reporting of Pregnancy

Any pregnancy where the estimated date of conception occurs either prior to the End of Study must be reported.

If an adverse outcome of a pregnancy is suspected to be related to study drug exposure, this should be reported regardless of the length of time that has passed since the exposure to study treatment. The medical monitor may decide that unblinding of the patient treatment assignment may be necessary.

An induced abortion or a spontaneous abortion is considered to be an SAE and should be reported in the same timeframe and in the same format as all other SAEs.

Pregnancies must be reported as soon as possible but no later than one business day by email.

All pregnancies must be followed to outcome. The outcome of the pregnancy must be reported as soon as possible but not later than 24 hours of the investigational site's knowledge of the outcome.

8. PHARMACOKINETIC ASSESSMENTS

Not applicable.

9. SCHEDULE OF ASSESSMENTS AND PROCEDURES

The assessments and procedures for this study are described in detail below and presented in the Schedule of Assessments and Procedures located behind the Synopsis.

9.1 Study Evaluation Timepoints

9.1.1 Screening (within 14 days prior to Baseline Day 1)

Potential study patients will be recruited by the study staff from patients. The following assessments will occur prior to study enrollment:

- Informed consent (study procedures or assessments may be performed prior to consent as many screening study procedures were obtained as part of the patient's standard of care treatment).
- Demographic Information
- Medical History
- Physical Exam

- Prior Medication History
- Chest CT or Chest X-ray
- Inclusion/Exclusion Eligibility Assessment (including assessment of shortness of breath within the last 14 days)
- Serum/Urine Pregnancy Test (if woman of childbearing potential)
- Clinical Laboratory Sampling to include: Full Chemistry Panel including LFTs, CBC with Diff including neutrophils and lymphocytes, PT/PTT, troponin, and BNP (Triglycerides, LDH, ferritin, fibrinogen, CRP, ESR, IL 6 and D-Dimer may be collected if the subject's condition warrants it)
- COVID-19 diagnostic test such as molecular or antigen test (However the COVID test was obtained, documentation of the results must be available prior to study entry. For additional study COVID tests, whenever possible, please use the same type of test)
- Vital Signs
- Height & Weight (If height can't be obtained, use the best reported historical height)

9.1.2 Days 1-10 Treatment

9.1.2.1 Randomization

- Evaluate that the patient continues to be eligible for the study by assessing Inclusion/Exclusion Criteria.
- Once eligibility has been confirmed, a Subject number beginning with 101 and rising sequentially will be assigned to the next enrolled subject.
- A blinded order for the Investigational Drug Services group will be generated by EPIC for the next sequential subject to be randomized.
- The unblinded pharmacist will prepare the treatment assignment (Active or Control) for the next assigned Subject number.
- The reconstituted study drug will be protected from light and labelled in a blinded manner to ensure maintenance of the study blind.
- Subjects will be randomized to receive either Active or Control for a maximum of 10 days, as clinically indicated and at the discretion of the Investigator.

9.1.2.2 Baseline-Day 1 (0 Hour)

- Continue evaluation eligibility by assessing Inclusion/Exclusion Criteria.
- Study drug treatment will begin at a starting dose of 13.6 ng/kg/min based on the concentration used to calculate Active treatment in mL/hr and can be titrated up to 30.6 ng/kg/min or down to 3.4 ng/kg/min as clinically warranted. The B.Braun syringe pump will be set to the appropriate dose in mL/hr utilizing the subject's sex and height (ideal body weight).
- Vital signs will be assessed twice daily in AM and PM while on study drug. Efforts will be made to obtain vital signs at the same time each day. Vital signs include: temperature, pulse rate, respiration rate and blood pressure.
- Adverse Event/SAE assessment daily

- Concomitant medication evaluation daily
- Continuous pulse oximetry (SpO₂)
- Ventilatory parameters assessed twice daily while on study drug: Ventilator Type, Vent Mode, FiO₂, Inspiratory time, Mean Airway Pressure, Peak Inspiratory Pressure, Positive End Expiratory Pressure, Tidal Volume, and Respiratory Rate
- Time Prone Position-16 hours per day per OSU Protocol

9.1.2.3 Day 1-12 hours

- Continue to administer study drug if clinically indicated.
- Adverse Event/SAE assessment daily
- Concomitant medication evaluation daily
- Oxygenation measurement via continuous pulse oximetry (SpO₂)
- Ventilatory parameters assessed twice daily while on study drug: Ventilator Type, Vent Mode, FiO₂, Inspiratory time, Mean Airway Pressure, Peak Inspiratory Pressure, Positive End Expiratory Pressure, Tidal Volume, and Respiratory Rate
- Vital signs will be assessed twice daily in AM and PM. Efforts will be made to obtain vital signs at the same time each day. Vital signs include: temperature, pulse rate, and blood pressure.
- Time Prone Position-16 hours per day per OSU Protocol

9.1.2.4 Days 2-10 (While on study drug)

- Continue to administer study drug if clinically indicated.
- Adverse Event/SAE assessment daily
- Concomitant medication evaluation daily
- Oxygenation measurement via continuous pulse oximetry (SpO₂)
- Ventilatory parameters assessed twice daily: Ventilator Type, Vent Mode, FiO₂, Inspiratory time, Mean Airway Pressure, Peak Inspiratory Pressure, Positive End Expiratory Pressure, Tidal Volume, and Respiratory Rate
- Vital signs will be assessed twice daily in AM and PM. Efforts will be made to obtain vital signs at the same time each day. Vital signs include: temperature, pulse rate, and blood pressure.
- Time Prone Position-16 hours per day per OSU Protocol

- Chest X-ray (Days 3-8 as clinically indicated)
- Full Chemistry Panel including LFTs, CBC with Diff including neutrophils and lymphocytes, PT/PTT, troponin, and BNP(Days 5 & 10).
- Triglycerides, LDH, ferritin, fibrinogen, CRP, ESR, IL 6 and D-Dimer may be collected if the subject's condition warrants it at Days 5 and Day 10.
- Obtain weight. (Day 10 only or at end of study drug dosing)

9.1.2.5 Weaning

See Section 5.3.4 and Table 3 for weaning guidelines.

9.1.3 Day 28/End of Study (EOS)

- Assess AEs/SAEs
- Assess Mortality
- Assess concomitant medications

9.2 Data Collection

Investigator or designee will enter the information required by the protocol onto source documents and enter data into data collection forms (DCFs) in an excel spreadsheet provided by Aerogen Pharma.

9.3 Clinical Data Management

Data from source documents will be verified against the DCF and any discrepancies will be clarified and resolved with study staff.

9.4 Database Quality Assurance

All data will be remotely monitored by the Sponsor due to the COVID-19 pandemic. Should restrictions be lifted at OSU, an on-site visit may occur if all parties are in agreement.

10. STATISTICAL CONSIDERATIONS

10.1 Statistical Methods

A Statistical Analysis Plan will be not be developed as this is an exploratory trial. Any statistical evaluation will be handled internally by Aerogen Pharma or their designee.

10.2 Determination of Sample Size

The number of patients has been selected to enable an adequate clinical assessment of pharmacodynamics, safety, and tolerability parameters without presenting undue risk to a large number of patient's being exposed to this investigational product.

10.3 Analyses Sets

All patients who are enrolled in the study and who receive at least one dose of study drug will be included in the intent-to-treat (ITT) analyses of pharmacodynamic and safety data. All available data will be used and missing data will not be estimated or carried forward in any statistical summary or analyses.

Descriptive summary statistics include the number of patients, mean, median, percent coefficient of variation (% CV) (if required), standard deviation, and minimum and maximum values (quantitative variables) or the number of patients and percentages by category (qualitative variables). Changes will be assessed as the difference between baseline measurements and the appropriate post-dose measurements unless otherwise specified. Mean differences between active and control groups (when available) will be assessed and significance will be determined on the basis of a 95% CI. Individual patient listings of data will also be provided to allow for review of all pharmacodynamic, safety, and tolerability parameters.

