2.1 Introduction

COVID-19 is a rapidly emerging pathogen that has recently been declared a pandemic by the World Health Organization (WHO). No targeted therapeutic treatments for coronavirus (COVID-19) have been identified. Symptoms range from mild upper respiratory tract infection to profound hypoxia, severe pneumonia, ARDS and death. Progression of end stage disease is unpredictable with high fatality rates in mechanically ventilated patients as a result of multi-organ failure. Among patients who require hospitalization, mortality may be 5% to 15%, and for those who become critically ill, reported mortality ranges from 22% to 62%.

Prostacyclin therapy—available in oral, inhaled, and intravenous forms—is an analogue which mimics endogenous prostacyclin (PGI2). Prostacyclin binds to its receptor (a G-protein coupled receptor) found on the surface of vascular smooth muscle and platelets, activates cyclic adenosine monophosphate (cAMP), and results in inhibition of platelet aggregation, vascular smooth muscle relaxation and vasodilation of the pulmonary arteries (Mitchell, Ali et al. 2008). Prostacyclins are most commonly used in the treatment of PAH due to their potent vasodilatory effects. In addition, prostacyclin analogs also inhibit platelet aggregation and may reduce prothrombotic effects of endothelin.

The rationale for use of vasodilators in COVID-19 patients rests on their rapid local effect on the pulmonary vasculature, which has shown to lead to increased oxygenation in other diseases, such as PAH (Higenbottam, Wheeldon et al. 1984) and post-surgical PH (De Wet, Affleck et al. 2004). Epoprostenol has the additional advantage over inhaled nitric oxide in that it may be directly administered through a standard ventilator (closed-circuit).

The rationale for aerosolized prostacyclin use in COVID-19 patients experiencing hypoxia leading to cardiac failure is two-fold:

- (1) inhaled prostacyclin therapy has been used in the treatment of ARDS and has been shown to improve oxygenation and ventilation-perfusion mismatch (see Section 9). Prostacyclins, such as epoprostenol, promote pulmonary vasodilation via a cyclic adenosine monophosphate-mediated decrease in intracellular calcium (Figure 4). While it has not been associated with improved outcomes, such as mortality, and it's use in ARDS is off-label, it may be used in severe life-threatening hypoxemia refractory to conventional ARDS management, such as has been seen in COVID-19.

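### Day 5 oxygenation is compared only among patients still alive, ventilated and on drug, which tends to shrink a real effect; the end-of-treatment substitute at Day 10 is undefined

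*Combined protocol and SAP*

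**What the plan says.** References are to the last, double-blind version in the combined file.

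- **Missing data (10.3):** "All available data will be used and missing data will not be estimated or carried forward in any statistical summary or analyses".
- **Comparison (10.3):** "Mean differences between active and control groups (when available) will be assessed and significance will be determined on the basis of a 95% CI".
- **Analysis set (10.3):** "All patients who are enrolled in the study and who receive at least one dose of study drug will be included". The set is labelled ITT.
- **Collection:** SpO2 and ventilator data after Day 1 sit under the heading "Days 2-10 (While on study drug", closing bracket omitted here. Section 9.1.2.2 has "Ventilatory parameters assessed twice daily while on study drug", and these parameters include the FiO2 needed for S/F and P/F.
- **Length of dosing (9.1.2.1):** "for a maximum of 10 days, as clinically indicated and at the discretion of the Investigator". Section 5.4.2 requires a positive-pressure ventilator mode for the device to deliver drug. Section 4.4.1 allows removal for worsening oxygenation or need for VV ECMO.
- **Endpoints (10.6.1, 10.6.2):** changes in S/F and P/F enter the primary failure definition and the secondary oxygenation responder definition. Both let the end-of-treatment value serve for Day 10. Section 4.4 asks for End of Treatment procedures in patients who discontinue before Day 10.
- **After treatment:** Day 28 (9.1.3) records adverse events, mortality and concomitant medication only. Section 10.1 says that no SAP will be written.

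**The concern.** A patient has no Day 5 value if he or she has died, has been extubated, or has been taken off drug for deterioration. The first and third groups are the sickest and the second is the best. Each exit is itself an outcome that epoprostenol is meant to influence. A mean over the remaining patients therefore no longer compares the randomised groups. A drug that keeps sicker patients alive adds low values to its own arm, and one that speeds extubation removes high values from it. Nothing says how death, extubation, ECMO or stopping drug enters the oxygenation comparison, and with no SAP planned no later document will settle it. At stake is the oxygenation signal that would inform further development.

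**Working it through.** **Step 1. Who has a value?**

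| Status at the time point | Day 5 under 9.1.2.4 | Day 5 under Table 2 and 7.1.1 | Day 10 |
|---|---|---|---|
| Dead | none | none | no rule |
| Extubated, alive | none | ventilator FiO2 has ended | end-of-treatment value possible |
| Off drug, still ventilated | none | value possible | end-of-treatment value possible |
| Ventilated and dosed | value | value | value |

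The choice between the two Day 5 readings affects only the third row. Death and extubation select the Day 5 set under either.

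**Step 2. Model.** The plan states no effect size, SD or power, so there is no figure to reproduce. Let oxygenation change be Y = δ + ε with SD 1 in each arm (δ = 0 in Control). A prognosis score correlates r with ε and is shifted by d in Active. The lowest scores die and the highest are extubated. With Control cut-points a = Φ⁻¹(share dead) and b = Φ⁻¹(1 − share extubated), the mean score of those left is

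m(a, b) = [φ(a) − φ(b)] / [Φ(b) − Φ(a)],

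and the available-case difference is

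D = δ + r × [m(a − d, b − d) − m(a, b)].

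**Inputs.** The 22% and 62% death shares are the ends of the range in Section 2.1 ("for those who become critically ill, reported mortality ranges from 22% to 62" percent), which carries no time point. All other event shares, r, δ and d are assumptions.

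**Step 3. Equal effect on prognosis and oxygenation (δ = d = 0.5 SD).**

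| Control dead / extubated | m Control | m Active | D, r = 0.5 | D, r = 0.8 | D, r = 1 |
|---|---|---|---|---|---|
| 22% / 0% | 0.380 | 0.198 | 0.41 | 0.35 | 0.32 |
| 62% / 0% | 1.002 | 0.678 | 0.34 | 0.24 | 0.18 |
| 22% / 20% | 0.028 | −0.374 | 0.30 | 0.18 | 0.10 |
| 22% / 40% | −0.237 | −0.696 | 0.27 | 0.13 | 0.04 |
| 40% / 20% | 0.266 | −0.186 | 0.27 | 0.14 | 0.05 |
| 10% / 50% | −0.559 | −0.998 | 0.28 | 0.15 | 0.06 |

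For example, row four at r = 0.8 is 0.5 + 0.8 × (−0.696 + 0.237) = 0.13. Across r = 0.5 to 0.8 the range is 0.13 to 0.41 SD, a loss of 18% (1 − 0.41/0.5) to 74% (1 − 0.13/0.5). At r = 1, splits of 20/20, 30/20, 30/30 and 40/20 give 0.11, 0.07, 0.04 and 0.05 SD. That is the extreme case.

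**Step 4. When does the sign change?** Set d = 2δ = 1.0 with δ = 0.5. At r = 0.5 all six splits stay positive (0.04 to 0.35). At r = 0.8 the two deaths-only splits stay positive (0.03 and 0.27), and the four with both exits give −0.15 to −0.23.

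If the drug affects mortality alone (δ = 0, no extubation), D = r × (difference in φ(z)/(1 − p)), where p is the share dead and z = Φ⁻¹(p).
- Mortality 40% to 20%: r × (0.350 − 0.644), so −0.15, −0.24 and −0.29 SD at r = 0.5, 0.8 and 1.
- Mortality 22% to 11%: r × (0.211 − 0.380), so −0.08, −0.13 and −0.17 SD.

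With δ = d = 0, D = 0, so the model creates no false benefit.

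**Step 5. Precision.** The 95% half-width is t × √(2/n): 2.101 × 0.447 = 0.94 SD at 10 per arm, 1.07 at 8 and 1.73 at 4.

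**Step 6. Ranking everyone.** A simulation ranked deaths worst, extubated survivors best and the rest by oxygenation. For a true 0.5 SD effect the probability that an Active patient does better was 0.61 to 0.64 with d = δ, and 0.66 to 0.73 with d = 2δ (null 0.50). The direction was right in every scenario, including those where D was negative. ECMO and reintubation were not modelled.

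**The case against.** The strongest reply concerns Day 10. The endpoints admit an end-of-treatment value, Table 2 heads its last treatment column accordingly, and Section 4.4 requires those procedures in early discontinuers. That stands: a reader might infer that Day 10 is also confined to patients still dosed, and the text does not support it. The substitute raises a different problem, since it pools values from different days, conflicts with a rule against carrying data forward, and says nothing about deaths.

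The on-drug limit is also less firm than the 9.1.2.4 heading suggests. Table 2 marks every day, its footnote ties ventilator data to twice-daily vital signs, and 7.1.1 takes vital signs on Days 1 to 10. This is a contradiction to reconcile, but it does not bring back the dead or the extubated.

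Failure to extubate and ECMO count in the primary endpoint, time to extubation and 28-day mortality are separate endpoints, and individual listings are promised. So the events are recorded and visible, but the oxygenation mean is still judged by its own interval.

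The secondary oxygenation endpoint is a responder definition, and the sizes above are for mean differences. That stands: the effect on the responder endpoint has not been computed.

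Finally, this is an exploratory trial. At 10 per arm, power for 0.5 SD is about 20% (Φ(0.5 × √5 − 1.96) = Φ(−0.84)), so such an effect would usually be missed even with complete data. That limits the practical weight but does not excuse an estimate that is off target.

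**Conclusion.** The point holds for Day 5, and for Day 10 in the narrower sense that the substitute value is undefined and deaths have no rule. At 12 hours no selection problem has been shown.

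The expected distortion is attenuation. The 0.13 to 0.41 SD for a true 0.5 SD rests on a normal model, assumed event shares and correlations of 0.5 to 0.8.

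A reader might infer more, and the documents do not support it:
- **That about 80% of an effect is lost.** That comes from r = 1 with 20% dead and 20% extubated (0.11 SD of 0.5), and nothing in the plan implies perfect correlation.
- **That reversal is to be expected.** It needs a larger effect on death or extubation than on oxygenation, or an effect on mortality alone.
- **That only 4 to 6 of 10 per arm contribute.** This follows entirely from assumed splits. The 22% to 62% mortality is not a Day 5 rate, and patients not expected to survive 48 hours are excluded.

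**What to change.** 1. **9.1.2.4 and Table 2:** collect charted SpO2/FiO2 and ventilator values to Day 10 for every randomised patient still in the ICU, on or off study drug. Reconcile the heading with Table 2 and 7.1.1.
2. **10.3:** in the oxygenation responder endpoint, count patients who die or go on ECMO before the time point as non-responders, and state a rule for patients extubated and alive.
3. **10.3, 10.6 and 4.4:** define end of treatment for analysis and reconcile its use as a Day 10 value with the rule against carrying data forward.
4. **10.3, Day 5 and Day 10 only:** add a ranked comparison of all randomised patients. Death or ECMO ranks worst, extubated and alive without reintubation best, reintubated patients by their observed value, and the rest by observed S/F or P/F. Keep observed-case mean differences as supportive.

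The cost is wording plus some chart abstraction at one site. The ranked result is not a mean difference, and it combines oxygenation with events that are also endpoints in their own right. That is partly a choice of question, which is why it is an addition and the mean differences stay. No change to clinical management is implied.
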